# 4. LIST OF ABBREVIATIONS

**BDP**; Biopharmaceutical Developmental Program CBER; Center for Biologics Evaluation & Research CED; convection-enhanced delivery CNS; central nervous system CPC: Cancer Protocol Committee CRM; continual reassessment method CSF; cerebrospinal fluid CTC; Common Toxicity Criteria DLT; dose-limiting toxicity DMEM; Dulbecco's minimal essential medium DNA: deoxyribonucleic acid DVT; deep vein thrombosis EGFRvIII; epidermal growth factor receptor (variant III) eCTD; electronic common technical document eIF; eukaryotic initiation factor FDA; Food and Drug Administration FLAIR; fluid-attenuated inversion recovery GBM; glioblastoma GCS; Glasgow coma scale Gd-DTPA; Gadolinium diethylene triamine pentaacetic acid HRV2; human rhinovirus type 2 HAS; human serum albumin IND; investigational new drug IRB; Institutional Review Board IRES; internal ribosomal entry site KPS; Karnofsky performance score MMSE; Mini-mental Status Examination MTD: maximally tolerated dose MVB: master virus bank NCI; National Cancer Institute Necl-5; nectin-like molecule 5 NHP; non-human primate NINDS; National Institute of Neurological Disorders and Stroke NSICU: Neuro-Surgical Intensive Care Unit OS; overall survival PET; positron emission tomography PFS; progression free survival PKC; protein kinase C PV1S; poliovirus serotype 1 (SABIN) RIO; research integrity office SAE: serious adverse event SIADH; syndrome of inappropriate antidiuretic hormone TCID; tissue culture infectious dose UTR; untranslated region WHO; World Health Organization

# 5. STUDY SYNOPSIS

Title:	DOSE-FINDING AND SAFETY STUDY OF AN ONCOLYTIC POLIO/RHINOVIRUS RECOMBINANT AGAINST RECURRENT WHO GRADE IV MALIGNANT GLIOMA							
Study	PVSRIPO administered intratumorally. PVSRIPO is the live attenuated, oral (SABIN)							
Agent:	serotype 1 poliovirus vaccine containing a heterologous internal ribosomal entry site							
-	(IRES) stemming from human rhinovirus type 2 (HRV2). PVSRIPO recognizes							
	nectin-like molecule-5 (Necl-5), an oncofetal cell adhesion molecule and tumor							
	antigen widely expressed ectopically in malignancy, e.g. glioblastoma (GBM), as host							
	cell receptor. Tumor specificity is mediated by selective expression of Necl-5 in GBM,							
	translation repression at the heterologous HRV2 IRES in the normal central nervous							
	system (CNS) and a supportive environment for PVSRIPO translation, growth and							
	cytotoxicity mediated by universally active protein kinase C (PKC)-Ras-Erk signaling							
	to translation machinery in GBM.							
Primary	To determine the MTD and the Phase II dose of PVSRIPO when delivered							
Objective:	intracerebrally by convection-enhanced delivery.							
Secondary	To obtain correlative mechanistic evidence for PVSRIPO's effects on infected WHO							
Objectives:	grade IV malignant glioma tumors and to estimate PFS and OS in recurrent WHO							
00,001,003.	grade IV malignant glioma patients.							
	To estimate the efficacy of PVSRIPO administered at the optimal dose.							
Exploratory	The primary exploratory objectives focus on outcomes associated with the initial							
Objectives:	PVSRIPO treatment:							
Objectives.	
 
Describe changes visualized on imaging due to intratumoral inoculation of
 
							
	PVSRIPO.							
	
 
Evaluate parameters of general immune activation: frequency of immune cell subsets in peripheral blood and changes in serum levels of cytokines.
 
							
	
 
Evaluate CD8 and CD4 immunologic response against polio specific and GBM specific antigens to be determined.
 
							
	
 
Identify genetic predictors of response or failure of response to treatment with PVSRIPO.
 
							
	Additional exploratory objectives focus on retreatment with PVSRIPO:							
	
 
Describe the toxicity of retreatment with PVSRIPO in combination with a single dose of lomustine.
 
							
	
 
Describe the PFS and OS of patients after retreatment with PVSRIPO and a single dose of lomustine.
 
							
	• Describe changes visualized on imaging after retreatment with PVSRIPO in combination with a single dose of lomustine.							
	• Evaluate parameters of general immune activation, including frequency of							
	immune cell subsets in peripheral blood, changes in serum levels of							
	cytokines, and CD8 and CD4 immunologic response against polio-specific							
	and GBM- specific antigens.							
Inclusion	Please see Section 9 for further details regarding eligibility.							
Criteria:	• Patients must have a recurrent supratentorial WHO grade IV malignant							
	glioma based on imaging studies with measurable disease ( $\geq 1$ cm and $\leq 5.5$							
	cm of contrast-enhancing tumor). Prior histopathology consistent with a							
	World Health Organization (WHO) grade IV malignant glioma confirmed by							
	the study pathologist, [name], or his designate.							
	• Age $\geq$ 18 years of age at the time of entry into the study.							
	• Karnofsky Performance Score $\geq$ 70%.							
	
 
Prothrombin and Partial Thromboplastin Times ≤ 1.2 x normal prior to biopsy.
 
							

	• Total bilirubin, SGOT, SGPT, alkaline phosphatase $\leq 2.5$ x normal prior to
	biopsy.
	
 
Neutrophil count ≥ 1000 prior to biopsy.
 

	
 
Hemoglobin ≥ 9 prior to biopsy.
 

	
 
Platelet count ≥ 125,000/µl prior to biopsy; Platelet count ≥ 100,000/µl prior to infusion.
 

	
 
Creatinine ≤ 1.2 x normal range prior to biopsy.
 

	• Positive serum anti-poliovirus titer prior to biopsy (except for retreatment).
	
 
The patient must have received a boost immunization with trivalent inactivated IPOL™ (Sanofi-Pasteur) at least 1 week prior to administration of the study exect.
 

	the study agent.
	
 
At the time of biopsy, prior to administration of virus, the presence of recurrent tumor must be confirmed by histopathological analysis.
 

	
 
A signed informed consent form approved by the Duke University Institutional Review Board (IRB) will be required for patient enrollment into the study. Patients must be able to read and understand the informed consent document and must sign the informed consent indicating that they are aware of the investigational nature of this study.
 

	
 
Able to undergo brain MRI with and without contrast.
 

Exclusion	Because of the unknown risk of virus administration potentially affecting a
Criteria:	developing fetus or growing infant, females who are pregnant or breast-
	feeding will be excluded. Adults of reproductive potential not employing an
	effective method of birth control will be excluded. Sexually active women of
	child bearing potential, whose partner is male, must use medically accepted
	birth control. Sexually active men, whose partner is a female of child bearing potential, must use a medically accepted birth control.
	
 
Patients with an impending, life-threatening cerebral herniation syndrome,
 

	
 
Patients with an impending, methodatening cerebral hernation syndrome, based on the assessment of the study neurosurgeons or their designate, will be excluded.
 

	Because the potential toxicities from the agent being studied in this protocol
	may be similar to some known diseases or may be more dangerous in the context of certain known diseases, the following patients will be excluded:
	
 
Patients with an active infection requiring intravenous treatment or having an unexplained febrile illness (Tmax > 99.5 F/37.5 C),
 

	
 
Patients with known immunosuppressive disease or known human immunodeficiency virus infection,
 

	
 
Patients with unstable or severe intercurrent medical conditions such as
 

	severe heart (New York Heart Association Class 3 or 4) or known lung
	(FEV 1 < 50%) disease, uncontrolled diabetes mellitus,
	
 
Patients with albumin allergy,
 

	
 
Patients with Gadolinium allergy.
 

	Patients with a previous history of neurological complications due to poliovirus
	infection will be excluded.
	
 
Patients who have not recovered from the toxic effects of prior chemo- and/or radiation therapy will be excluded. Guidelines for this recovery period are dependent upon the specific therapeutic agent being used.
 

	
 
Patients may not have received chemotherapy or bevacizumab ≤ 4 weeks
 

	[except for nitrosourea (6 weeks) or metronomic dosed chemotherapy such
	as daily etoposide or cyclophosphamide (1 week)] prior to starting the study
1	drug unless patients have recovered from side effects of such therapy.

	
 
Patients may not have received immunotherapy ≤ 4 weeks prior to starting the study drug unless patients have recovered from side effects of such therapy.
 
Patients may not be less than 12 weeks from radiation therapy, unless progressive disease outside of the radiation field or 2 progressive scans at least 4 weeks apart or histopathologic confirmation.
 
Patients must have completed all standard of care treatments, including surgical procedure and radiation therapy (at least 59Gy)
 
o If the MGMT promoter in their tumor is known to be unmethylated, patients are not mandated to have received chemotherapy prior to participating in this trial.
 
o If the MGMT promoter in their tumor is known to be methylated or the MGMT promotor methylation status is unknown at the time of screening, patients must have received at least one chemotherapy regimen prior to participating in this trial.
 
Because of the potential toxicities from the agent, patients with neoplastic lesions in the brainstem, cerebellum, or spinal cord, radiological evidence of active (growing) multifocal disease, or leptomeningeal disease will be excluded. Patients with evidence of diffuse subependymal disease or tumor in the brainstem, cerebellum, spinal cord, or CSF will also be excluded.
 

	
 
Patients with the following will be excluded:
 
Undetectable anti-tetanus toxoid IgG (except for retreatment).
 
Known history of agammaglobulinemia.
 
Patients on greater than 4mg per day of dexamethasone within the 2 weeks prior to admission for PVSRIPO infusion.
 
Patients with worsening steroid myopathy (history of gradual progression of bilateral proximal muscle weakness, and atrophy of proximal muscle groups).
 
Patients with prior, unrelated malignancy requiring current active treatment with the exception of cervical carcinoma in situ and adequately treated basal cell or squamous cell carcinoma of the skin.
 

Study Design:	This protocol is designed primarily to determine the MTD and DLT of a novel oncolytic viral recombinant with GBM-specific viral translation, replication and cytotoxicity. PVSRIPO will be delivered intratumorally by convection-enhanced delivery using an intracerebral catheter placed within the enhancing portion of the tumor. To enable tracking of the inoculum, 1 mM Gadolinium will be co-infused. The contrast agent (Gd-DTPA) will be added to the virus-containing infusate. Based on pre-clinical toxicity studies in non-human primates, the starting amount of the agent to be delivered will be 1 x 10  tissue culture infectious dose (TCID50). Due to limitations imposed by manufacture and dosing volume in Cynomolgus macaques, the MTD was not reached in non-human primates. Intra-thalamic inoculation of 5 x 10  TCID in Cynomolgus macaques did not cause any toxicity. A total of 3 mLs of the agent in physiologic saline stabilized with 0.2% human serum albumin will be delivered over approximately 6 hrs 30 minutes, corresponding to a flow-rate of 0.5 mL/hr. The agent is stable at room temperature during the intended instillation period and the intended delivery apparatus is not associated with adsorptive loss of PVSRIPO. PVSRIPO dose escalation will be accomplished by increasing agent concentration allowing flow-rate and infusion volume to remain constant.
	A two-step continual reassessment method design will be used for dose escalation. Starting at dose level 1, one patient will be treated at each dose level. Decisions concerning dose escalation for subsequent patients will be based upon the occurrence of DLT during the first 4 weeks after treatment administration. Initially,

each patient will be observed for  $\geq$  4 weeks before the next patient is treated. If no patients experience a DLT on the first 4 dose levels, all subsequent patients will be treated at dose level 5. Escalation will be interrupted if any of the patients assigned to one of the first 4 dose levels or  $\geq$  20% of patients treated at dose level 5 experience a DLT. In that case, further dose escalation or de-escalation will be guided by the likelihood-based implementation of the continual reassessment method. Greater detail is provided in section 11.1.5.1.

Historical Modifications to the Protocol:

As of 11/15/2013 (AMD025), 4 patients have been treated on dose level 5. One patient experienced a DLT upon removal of the treatment catheter. The remaining 3 patients have not experienced a DLT; however, all 3 have had difficulties tapering off steroids. To address this concern, the study is amended to reduce the dose for the next cohort of patients to dose level 2. Up to 6 patients will be accrued at dose level 2. If 2 of these patients experience a DLT as defined in section 11.4, accrual will be suspended.

As of 6/5/14 (AMD041), 5 subjects have been treated on dose level 2. Four subjects have completed the two-week follow-up period and have not had a DLT. One subject remains in the 14 day follow up period. Once one last patient has been treated, the study per the November 2013 amendment is complete. We are amending the study to allow continued patient accrual to garner more information about patient safety while the single-institution phase 2 study is being developed and reviewed by various regulatory bodies. We intend to continue accruing subjects for treatment at dose level 2 until such time that the phase 2 study has been activated. After each patient has been followed for a one-week observation period, during which the patient will have been evaluated in clinic on day 7 (± 2 days), a patient summary will be prepared and submitted to the DSMB chair for approval. Once approval from the DSMB chair has been obtained, treatment of the next patient will be allowed. We will treat up to four subjects within a 30-day period as allowed by DSMB chair, and there will be only one PVSRIPO treatment per patient without specific approval for a second or more treatments from the FDA and the IRB.

As of 10/06/2014 (AMD048), 7 subjects have been treated on protocol at dose level 2. One additional subject has been treated under a Single Subject Emergency Use Request at dose level 2. Of these eight subjects, six subjects had difficulty or remained unable to be tapered off steroids more than three months post infusion (three subjects required the addition of bevacizumab to facilitate the taper down or off steroids). We are amending the study to reduce the dose to dose level -1 (5.0 X 10^7 TCID50) with the goal of limiting the occurrence of known possible side effects of prolonged steroid use in patients who otherwise benefit from this investigational therapy. This dose reduction will allow continued patient accrual and garner more information about patient safety and optimal dosing while the single-institution phase 2 study is being developed and reviewed by various regulatory bodies. Our last amendment allowed the enrollment of up to 18 patients, one patient was enrolled under that amendment and thus, we are planning to enroll up to 17 patients on dose level -1. After each patient has been followed for a one-week observation period, during which the patient will have been evaluated in clinic on day 7 ( $\pm$  2 days), a patient summary will be prepared and submitted to the DSMB chair for approval. Once approval from the DSMB chair has been obtained, treatment of the next patient will be allowed. We will treat up to four subjects within a 30-day period as allowed by DSMB chair, and there will be only one PVSRIPO treatment per patient without specific approval for a second or more treatments from the FDA and the IRB.

Study Design Modification (1/13/2015 AMD054)). Once the optimal dose level of PVSRIPO is determined, a total of 26 patients will be treated at that dose level on a dose expansion cohort. The survival associated with these 26 patients will be compared to that of a historical cohort (see section 14.3). The study is being amended to allow accrual and treatment of a total of 26 patients at the optimal dose level of PVSRIPO and, as needed, radiation-necrosis dose levels and schedules of bevacizumab to estimate the efficacy of PVSRIPO relative to a historical cohort.

Sample Size Modification (6/24/2015 AMD071). As of 6/24/15, we have treated 13 patients on dose level -1. None of the patients have had prolonged steroid needs, two patients died at 3 and 6 months respectively, and five patients total (including the two patients who died) were initiated on bevacizumab. It is now felt that dose level -1 is the optimal dose, as none of the patients have experienced undue side effects due to PVSRIPO or the management of the cerebral inflammation secondary to PVSRIPO. We are now amending the protocol to enroll a total of 50 patients on dose level -1.

Study Design Modification (11/10/2015 AMD078). Imaging response criteria were previously developed based on imaging observations following chemoradiation treatment (Macdonald criteria) and subsequently revised based on new observations from anti-angiogenic trials (RANO criteria). As imaging is dramatically different following treatment with immunotherapy, new imaging criteria are being developed (iRANO). This process is likely to take several years to validate. For that reason, we are removing response rate as a secondary objective and adding, as an exploratory objective, a description of changes visualized on imaging due to intratumoral inoculation of PVSRIPO.

Study Design Modification (2/1/2016 AMD081). The protocol has been re-formatted in an electronic Common Technical Document (eCTD) format for electronic submission to the FDA for the associated IND. The statistical section has been revised and an appendix (section 18.4) has been added to define and describe the historical control group being used as a statistical comparison for the subject population. We have also further described the types of subject follow-up activity that will occur in this study.

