Study Design Modification (9/5/2016 AMD104). This amendment includes the addition of an exploratory objective to identify genetic predictors of response or failure of response to treatment with PVSRIPO. Molecular genetic tests, such as, but not limited to, DNA sequencing, gene amplification, and gene expression, will be performed on the tissue obtained at the protocol-specified biopsy prior to PVSRIPO infusion. Tissue may be obtained for testing as either fresh, frozen, or fixed tissue, or as slides, after the diagnostic pathologist has retained all tissue needed for diagnosis. The amount of tissue required for this testing should be sufficient to yield a minimum of one microgram of DNA.

Study Design Modification (3/1/2017 AMD124). Based upon recent pre-clinical data and clinical data collected on dose levels -1 and -2, we have concluded that there is no evidence of pre-clinically or clinically important differences between these dose levels. The initial need for treatment with the radiation necrosis dose levels and schedules of bevacizumab for cerebral inflammation secondary to PVSRIPO or tumor growth has been comparable thus far. In addition, the toxicity profiles for the two dose levels are also similar. Therefore, we have decided to proceed with the development of PVSRIPO dose level -1 (5.0 X 10^7 TCID50) within the phase II study that is now in development. We are amending this phase I study to treat all future patients at the -1 dose level. We intend to continue accruing patients and treating patients at this dose level while the phase II study is being finalized and reviewed by various regulatory bodies.

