## 9. STUDY POPULATION

#### 9.1. INCLUSION CRITERIA

#### 9.1.1. Disease Status

Patients must have a recurrent supratentorial WHO grade IV malignant glioma based on imaging studies with measurable disease ( $\geq$  1 cm and  $\leq$  5.5 cm of contrast-enhancing tumor). Prior histopathology consistent with a World Health Organization (WHO) Grade IV malignant glioma confirmed by the study pathologist, [name], or his designate.

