#### 11.1.2. Agent Infusion

The entire volume of the agent to be delivered will be pre-loaded into a syringe by the investigational pharmacist and connected to the catheter under sterile conditions in the Neuro-Surgical Intensive Care Unit (NSICU) or neuro step down unit just prior to beginning of infusion. Due to the complexity of scheduling all of the necessary components for the infusion (operating room time, pharmacy time, and radiology appointments), a +1 day window has been built in to the study for the study drug infusion. This means that the infusion is allowed to start the following day after the biopsy/catheter placement. This will still be considered "day 0" in regards to the protocol and the timing of the subsequent events. At the time of virus injection, emergency drugs, including epinephrine and diphenhydramine will be available and the neurologic status, oxygen saturation, and cardiac rhythm will be monitored. Drug infusion will occur in the Neuro-Surgical Intensive Care Unit (NSICU) or neuro step down unit so that all other emergency facilities will be available. Patients will be treated with appropriate antibiotic prior to biopsy and catheter insertion per DUHS Neuro-surgical standard practice.

Based on our own experience, previously published reports (38) and IRB- and FDAapproved trials using similar infusion techniques (IRB# 4774-03-4R0), patients will be infused at a rate of 500  $\mu$ L/hr. A Medfusion 3500 or 3010 infusion pump will be preprogrammed to a delivery rate of 500  $\mu$ L/hr. The agent (which will be in a total volume of 8 mL to account for 'dead-space' of 3.3723 mL in the infusion system) will be loaded in a 20 mL syringe into the syringe pump at the initial onset to avoid any interruptions in the infusion. The total amount of the inoculum delivered to the patient will be 3 mL. The catheter itself (30 cm length, 1 mm interior diameter) cannot be preloaded with virus suspension. The infusion pump will be programmed for delivery of 500  $\mu$ L/hr per hour over approximately 6.5 hours. To account for the dead space, the pump will be stopped when the delivered amount is between 3.125 to 3.250 mL. The infusion will be performed using a Medfusion 3500 or 3010 (Smiths Medical ASD, Inc, Minneapolis, MN) syringe infusion pump. The virus injection procedure will be completed within approximately 6.5 hrs. The catheter will be removed following the post-PVSRIPO infusion MRI.

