#### 11.1.5. Dose

The anti-neoplastic effects of PVSRIPO in animal tumor models are dose-dependent. PVSRIPO produced complete tumor regress in all treated animals at a 'mouse-adjusted' dose equivalent to  $5 \times 10^8$  TCID50 [1/10th of the non-toxic dose in NHPs in the dose-range finding toxicology study (Table 1)]. 'Mouse-adjusted' means that the dose was 1/70th of 5 x 10^8 TCID50, since the starting tumor volume in athymic mice was 1/70th of the maximum tumor size in patients. Reducing this dose 100-fold significantly diminished the anti-neoplastic efficacy of PVSRIPO in animal tumor models.

Since no prior experience with intracerebral inoculation of PVSRIPO in humans exists, consideration of dose-escalation is based on the results of neurovirulence assessments in dose-range finding and biodistribution studies in non-human primates. These assessments evaluated the clinical outcome and toxicity after intrathalamic administration of PVSRIPO in *Cynomolgus* macaques (Table 1 & Table 2).

The highest dose in the definitive, IND-directed study in NHPs (1 x  $10^9$  TCID50; Table 2) was limited by the highest feasible concentration in an acceptable inoculation volume (limited to 250 µL in *Cynomolgus*). In this NHP study, DLTs were not observed and the MTD was not reached. Therefore, in this trial, based on pre-clinical NHP toxicity studies, the proposed starting dose is 1 x  $10^8$  TCID50, which is  $1/10^{th}$  of the highest non-toxic dose in NHPs in the definitive, IND-directed toxicology study (Table 2) and  $1/50^{th}$  of the highest non-toxic dose in NHPs in the dose-range finding toxicology study (Table 1).

PVSRIPO Dose	Equiv. Human Dose	No. of Animals	Route	Day of Sacrifice	Clinical Outcome
Vehicle	N/A	1	intrathalamic	3	no toxicity/neurologic symptoms
Vehicle	N/A	1	intrathalamic	21	
1 x 10  TCID50	1 x 10  TCID50	1	intrathalamic	3	
1 x 10  TCID50	1 x 10  TCID50	1	intrathalamic	21	
1 x 10  TCID50	1 x 10  TCID50	1	intrathalamic	3	
1 x 10  TCID50	1 x 10  TCID50	1	intrathalamic	21	
5 x 10  TCID50	5 x 10  TCID50	1	intrathalamic	3	-
5 x 10  TCID50	5 x 10  TCID50	2	intrathalamic	21	

 Table 1. Dose range-finding, toxicology, biodistribution and shedding study (BATTELLE Study 916-G663301) of PVSRIPO in Cynomolgus macaques

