Given that the study is not a randomized study, there is a need to statistically adjust survival comparisons for confounding factors. Hence, survival comparisons will be conducted using the Cox model. Predictors within the Cox model will include treatment, age, extent of resection, prior bevacizumab treatment, Karnofsky performance status at the time of PVSRIPO treatment, number of prior recurrences, and an indicator of secondary GBM.

It should be noted that the calculations and analyses described above assume that survival with PVSRIPO is exponentially distribution and that the proportional hazards assumption is satisfied. Recently reported studies suggest that such properties may not exist for immunotherapeutic agents due to (1) delayed antitumor effects and hence delayed separation of survival curves, and (2) a percentage of patients who are "cured" or survive for a relatively long period of time. If that is the situation with PVSRIPO, the power calculations and planned analyses may not be appropriate. It might be more appropriate to focus on long-term survivorship at a specific time point such as 18 and 24-month survival. Within the second historical control group, the 18 and 24-month survival probabilities are 23.1% and 13.5%, respectively. A two-tailed chi-square test ( $\alpha$ =0.2) conducted to compare the proportion of patients alive at 18 or 24 months at the 0.2 level has >84% power to detect an increase of 15% in survivorship. Logistic regression will be used to adjust for confounding factors.

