## 18.4. SELECTION AND DESCRIPTION OF THE HISTORICAL CONTROL COHORT

The historical cohort that will be used for the evaluation of PVSRIPO efficacy among WHO grade IV malignant glioma patients was derived from the PRoGREss registry (IRB# Pro00027120; Primary and Recurrent Glioma Registry).

Description of PRoGREss registry: The PRoGREss registry study is both a retrospective and prospective chart review study of all patients diagnosed after 12/31/2004 with a primary CNS tumor who were seen at the PRTBTC. Specifically, that database includes: (1) data from all patients that were deceased as of 11/3/2011, and (2) data collected retrospectively and prospectively from patients who were alive as of 11/3/2011 and provided registry consent. The latter group includes patients who were diagnosed after 12/31/2004 but before 11/3/2011, as well as patients diagnosed after 11/3/2011. Both demographic and clinical information was extracted from clinical and research records, which included such information as diagnosis, gender/race/ethnicity, medical history, medications, and types of treatment. Details about the data available from the PRoGREss registry can be found in the PRoGREss protocol.

Criteria Used to Select Historical Control Cohort: To create the historical cohort, data available from the PRoGREss registry as of 12/15/2014 were reviewed to determine which patients would have been eligible to participate in the PVSRIPO phase I study at the time their disease recurred in 2007 or later. All radiologic records were reviewed by [name] without knowledge of the patient's survival outcome in making this determination.

During the conduct of the PVSRIPO WHO grade IV malignant glioma Phase I study, most modifications to the patient eligibility criteria were minor. As such, the eligibility criteria used for identifying the historical control cohort from the PRoGREss registry were standardized. The following relevant criteria were used:

- 1. Patients must have a diagnosis of recurrent supratentorial WHO Grade IV MG based on imaging studies with measurable disease (≥ 1 cm and ≤ 5.5 cm of contrast-enhancing tumor)
- 2. Age  $\geq$  18 years of age
- 3. Patients must not have taken part in the PVSRIPO study
- 4. KPS ≥70 at the time patient could have been enrolled on the PVSRIPO study
- 5. Absence of rapid clinical decline

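### Baseline tumor size is missing from the listed Cox predictors and from the historical-control table, although it was judged on imaging in both groups and could confound the survival comparison

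*Combined protocol and SAP*

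**What the plan says.** **Dosing.** The synopsis states that "PVSRIPO dose escalation will be accomplished by increasing agent concentration allowing flow-rate and infusion volume to remain constant". Section 11.1.2 gives the volume: "The total amount of the inoculum delivered to the patient will be 3 mL".

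**Tumor size at entry.** The synopsis requires recurrent grade IV "glioma based on imaging studies with measurable disease". It and Section 9.1.1 set the limits at no less than 1 cm and no more than "5.5 cm of contrast-enhancing tumor". Criterion 1 in Appendix 18.4 applies the same limits to the controls. Their radiology was reviewed "without knowledge of the patient's survival outcome in making this determination".

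**Adjustment.** Section 14.3.1 says that the lack of randomisation creates a need for statistical adjustment. "Predictors within the Cox model will include treatment, age, extent of resection, prior bevacizumab treatment", followed by Karnofsky status, the count of earlier recurrences, and secondary versus primary GBM. Tumor size is absent. The logistic models for survival at 18 and 24 months (Sections 14.3.1 and 14.3.2) adjust for confounders that are not named.

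**Description of controls.** The Appendix 18.4 table covers sex, age, histology, primary or secondary GBM, Karnofsky status, resection, further surgery, progressions, steroid dose, bevacizumab and vital status. It has no tumor-size row.

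**Size and outcome.** Section 15.2.7 names tumor size among the factors that help to predict the risk from cerebral edema. No passage states how size relates to survival.

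**The concern.** The decision on whether dose level -1 merits further study rests on comparing treated patients with 104 registry controls. The validity of that comparison depends on the covariates. Size had to be judged on imaging in both groups to apply the entry criterion, so its omission does not look like a limit of the data.

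A shared 1 to 5.5 cm window bounds size but does not balance it. Three features could shift the distribution within the window:

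- The five control criteria in Appendix 18.4 do not list the trial's exclusions for growing multifocal disease and callosal extension (Section 9.2.6).
- Treated patients needed a site that allowed the catheter to sit at least 1 cm from the ventricles (Section 11.1.1).
- The clocks start differently: at the start of protocol treatment for patients (Section 13.3), and at the first MRI showing eligibility for controls (Appendix 18.4).

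If size also affects survival, the estimated treatment hazard ratio absorbs part of that effect and the nominal error rate no longer holds. Because size is not reported by group, no reader can check.

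**Working it through.** **Inputs from the documents.** One-sided level 0.20 (critical value 0.8416); 15 treated deaths at the end of accrual, rising to 30 after 12 more months (Table 4); 103 deaths among the 104 controls. The 0.20 level is stated for the log-rank test. I assume that it carries over to the treatment term of the Cox model.

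**Step 1: reproduce the plan's power.** With var(log HR) = 1/d + 1/103, the information is I = 1/(1/d + 1/103), and power = Φ(|ln HR|·√I − 0.8416).

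For d = 15, I = 13.09 and √I = 3.618. At HR 0.5: 0.693 × 3.618 − 0.842 = 1.666, so power is 0.952. The four hazard ratios give 0.952, 0.907, 0.843 and 0.763, against the printed 0.95, 0.91, 0.84 and 0.76. The other cells of Table 4 also reproduce, except 9 months at HR 0.55 (printed 0.9, computed 0.973, apparently a dropped digit). The variance formula is therefore the plan's own.

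**Step 2: false-positive rate if size is imbalanced and left out.** The documents give neither a size distribution nor a size-survival effect, so both are assumed. Let h be the death HR per cm and δ the mean amount by which treated tumors are smaller. With no true treatment effect, the apparent HR is h^(−δ), and

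false-positive rate = 1 − Φ(0.8416 − δ·ln h·√I).

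Example: h = 1.2, δ = 0.5 cm, d = 15. Then 0.5 × 0.1823 × 3.618 = 0.330, 0.8416 − 0.330 = 0.512, and the rate is 0.304. For d = 30, I = 23.23 and √I = 4.820.

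| HR per cm | Apparent HR (δ = 0.5 cm) | Rate, 15 deaths | Rate, 30 deaths |
|---|---|---|---|
| 1.1 | 0.953 | 0.252 | 0.270 |
| 1.2 | 0.913 | 0.304 | 0.344 |
| 1.3 | 0.877 | 0.357 | 0.417 |

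Widening δ to 0.25–1.0 cm gives 0.22 to 0.54 with 15 treated deaths and 0.23 to 0.66 with 30. With δ = 0 the rate is 0.20 throughout.

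**Step 3: the opposite direction.** If treated tumors are 0.5 cm larger, the false-positive rate falls below 0.20 and power is lost. For a true HR of 0.65 and h = 1.1, 1.2 and 1.3, power drops from 0.763 to 0.707, 0.651 and 0.596 with 15 deaths, and from 0.892 to 0.843, 0.787 and 0.727 with 30.

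**Step 4: cost of one more Cox term.** If size shares R² with treatment, the effective number of deaths is multiplied by (1 − R²). For R² = 0.02 to 0.10 and 15 treated deaths, power moves from 0.952 to 0.950–0.938 at HR 0.5, and from 0.763 to 0.758–0.738 at HR 0.65.

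**The case against.** The strongest reply is that no confounding has been shown. Size confounds only if it differs between groups and affects survival. Both groups share one size window, and the documents report neither an imbalance nor a size-survival effect. The calculation also treats the size effect as independent of the listed predictors; if size correlates with Karnofsky status or extent of resection, part of the bias is already removed. The plan names six adjusters, and the comparison is a screen at the 0.20 level. All of this stands, and it limits the point to a possible confounder. It does not explain why a baseline value judged in both groups is neither adjusted for nor reported.

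Four stronger readings are tempting but unsupported:

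- **That the protocol scales patient dose to tumor volume.** The words "since the starting tumor volume in athymic mice was" in Section 11.1.5 belong to a conversion of dose for mice. The human starting dose comes from primate toxicology, and nothing is scaled between patients.
- **That virus per mL of tumor makes dose levels interchangeable.** For spheres the eligible volumes could differ (5.5/1)³ = 166-fold, but that is a geometric extreme. It says nothing about group differences, it assumes that infusate spreads through the whole tumor, and it has no meaning for untreated controls. Constant-volume infusion is not itself an error.
- **That a model comparing levels -1 and -2 omits size.** Section 14 plans no such model; each level is compared with controls. The amendment's statement of "no evidence of pre-clinically or clinically important differences between these dose levels" is a narrative judgement from pre-clinical data, bevacizumab need and toxicity.
- **That size enters no model at all.** This is shown only for the Cox model. The logistic covariates are not listed, which is a gap of its own.

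**Conclusion.** The point holds in limited form and should be acted on. Section 14.3.1 commits to adjusting for confounders, yet baseline tumor size is missing from its listed Cox predictors and from the control table, although the entry criterion required it to be judged on imaging in both groups. It is a possible, unreported confounder of unknown direction.

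The illustrative range of 0.25 to 0.42 for the nominal 0.20 error rate rests wholly on assumed inputs: HR 1.1 to 1.3 per cm, treated tumors 0.5 cm smaller, and a size effect independent of the other covariates. It shows what modest imbalance could do, not what happened. The omission alone does not show that the treated-versus-control result is biased, and it supports no conclusion about dose.

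**What to change.** 1. Add baseline maximum enhancing diameter, or log volume, to the Cox predictors in Section 14.3.1. Take it from the screening MRI for treated patients and the index MRI for controls, and fix its form before analysis.
2. List the covariates of the 18- and 24-month logistic models and include size.
3. Report baseline size by dose cohort and for each control group in Appendix 18.4.
4. Because Section 15.2.7 links size to edema risk, describe bevacizumab use and toxicity at levels -1 and -2 by baseline size. This is descriptive only.

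**Cost.** In the Cox model, one term supported by at least 15 + 103 = 118 deaths, with the small power loss shown above. The logistic models are thinner. At level -2 the plan's own figures imply about 104 × 0.135 = 14 control and 27 × 0.35 = 9 treated survivors at 24 months, so that covariate list should be short and set in advance. If control diameters were not stored, they must be abstracted from 104 MRI records already reviewed, again blind to survival.
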